10.0 Procedures Involved

10.1 Describe and explain the study design.

Once a subject has been identified, the initial visit will be scheduled. During the experimental day, informed consent will be completed, and the subjects will complete the following tasks: (1) an investigator will conduct visual acuity assessments of both eyes (Snellen). (2) The subjects will be asked to complete a survey (on contact lens satisfaction). (3) After the survey, the subject will sit with their lenses for assessment using the Keratograph topographer. (4) After topography, slit lamp assessment of the rigid lenses, and then of the cornea and conjunctiva (after lens removal) with and without Lissamine Green staining will be done.

At visit one, the following additional task will be performed: (1) The subject will be asked to sit for a corneal or scleral lens fitting visit (based on what they wear habitually), where the investigator will fit the subject with a commercially available scleral or corneal lens. All subjects will be refit into the Advanced Vision Technologies (AVT) brand of rigid lenses, manufactured at AVT Technologies in Colorado. If they already wear the AVT brand, the lens parameters will simply be re-ordered. All lenses will undergo a diagnostic fit with an AVT lens. The parameters available at AVT are similar to those available at all other major labs in the US.

A second visit will be to evaluate the fit of the ordered study lenses (which will have been coated with the HydraPEG coating), and will be for the dispense of the lenses. In addition to evaluating the lenses, the subjects will be asked to complete a short survey on their satisfaction with their current lenses. After this visit, the subjects will then wear the lenses for 30 days, on a daily basis as they habitually would, cleaning the lenses with ClearCare hydrogen peroxide cleaning system, a commonly used commercially available soft and rigid contact lens cleaner. After 30 days of lens wear, they will report for visit 3.

At the third visit, the same testing will be performed from visits 1 and 2, the subject will also be given an additional survey regarding the satisfaction with the HydraPEG lenses, and then the Tangible Boost kit or the placebo kit (consisting of

Page 9 of 22 Revised: July 24, 2017

two vials with Unique pH) solutions will be dispensed (randomized) to store their lenses in for 30 minutes that night.

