The solution will be dispensed and the subjects trained on its use, and the subjects will be asked to store their lenses in the given solution for 30 minutes that evening, and then transfer their lenses to Unique pH multipurpose rigid lens solution for overnight storage. For the initial training with the Boost or placebo system, the users will undergo an approximately 60-minute user training in which there will be visual and audio recording and still photographs taken in order for a human factors company (Userwise) to analyze the usability of the product. The investigator at the study visit will act as the monitor for the training session. This recorded training step was specifically designed to allow for proper evaluation of the usability of the product, which they will report to the FDA to ensure usability. At the initial visit, the subject will have indicated on the informed consent form whether they agree to participate in the recorded portion of the training. If they do not participate in the recording, they can still be trained and participate in the study.

The subjects will report to the Ocular Surface Institute the next day for Visit 4, at which time the comfort and visit tests will occur again, and an additional survey to evaluate the boost treatment will be given. After visit 4, the subjects will continue to wear the study lenses daily for an additional 60 days, treating their lenses again in the Boost or placebo solution at the midpoint between visit 4 and 5 (30 days after the first treatment with Boost), otherwise cleaning nightly with ClearCare, and will then report to the clinic again 30 days after the midway treatment (approximately 90 days after the initial HydraPEG dispense). The same visit testing will be done at this final and 5th visit, and a final short survey will be done, and then the lenses will be collected from the subjects and sent back to Tangible Science, Inc. for their internal testing of the lenses (no involvement of the UH research team). At this time the study will conclude.

The following table outlines each of the study visits and tells what procedures will be done at each visit:

Procedure	Length of Time Required for	Frequency of Repetition
VISIT 1: Initial Evaluation		
Informed consent & HIPAA	35 minutes	Once
General History and medications	5 minutes	Once per visit
Visual Acuity	5 minutes	Once per visit

Page 10 of 22 Revised: July 24, 2017

Questionnaires (CLDEQ8 + VAS)	10 minutes	Once per visit

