Statistical Analysis: Each individual will act as their own control to measure differences in pre and post contact lens measurements (paired non-parametric statistics), and this baseline data will be compared to normative data available for a soft contact lens wearing population. Descriptive statistics will also be employed to evaluate the overall response of the eye to a rigid lens with and without HydraPEG and with and without Tangible Boost.

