24.0 FERPA - N/A

25.0 Data Management

25.1 Describe the data analysis plan, including any statistical procedures.

Data will be stored in a study paper file. Paper files will be kept in a filing cabinet within The Ocular Surface Institute (Health and Biomedical Sciences Building). Electronic data will be stored on a password-protected computer in a locked office in rooms 232, 236 or 250 within The Ocular Surface Institute of the Health Biological Sciences Building (HBSB). All study data will remain on UH property within The Ocular Surface Institute for a minimum of 3 years following study completion. The principal investigator will be

Page 20 of 22 Revised: July 24, 2017

responsible for maintaining study data security and subject confidentiality, and the PI and the study coordinator will be responsible for receipt and transmission of the data. The investigative team, study sponsor and inspectors from regulatory agencies such as the US Food and Drug Administration will have access to the data if requested for study monitoring or an audit.

All collected data will be documented on study documents and analyzed for differences between baseline and test data. Hypothesis testing will be performed using statistical analyses including parametric or nonparametric comparisons (i.e., t-tests, signed-rank tests), analysis of variance, general linear models, correlation, or regression techniques.

The recorded audio and video data will be sent to UserWise for analysis of the usability of the product.

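### Subjects are randomized to Boost or placebo, but no test between the arms is named; the paired within-person analysis cannot separate Boost from shifts common to both arms

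*Combined protocol and SAP*

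**What the plan says.** **Design (10.1).** At Visit 3 each subject is given, at random, a Boost kit or a placebo kit of "two vials with Unique pH". The allocation ratio is not stated. Both arms soak the lenses for 30 minutes that evening, "then transfer their lenses to Unique pH multipurpose rigid lens solution for overnight storage", and return the next day for Visit 4. A second treatment follows 30 days after the first, and Visit 5 comes 30 days after that.

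**Analysis (10.2 and 25.1).** Section 10.2 states: "Each individual will act as their own control to measure differences in pre and post contact lens measurements", using paired nonparametric statistics. Descriptive statistics then cover the response to a lens "with and without HydraPEG and with and without Tangible Boost". In 25.1 the data are to be "analyzed for differences between baseline and test data", and the tests listed are "parametric or nonparametric comparisons (i.e., t-tests, signed-rank tests), analysis of variance, general linear models", correlation or regression. Neither section names a comparison of Boost with placebo, a pair of visits or an endpoint for the test. The hypothesis in 1.2 and the preference item on the follow-up surveys are also framed as before and after treatment.

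**Lens care.** From Visit 2 to Visit 3, 10.1 has subjects "cleaning the lenses with ClearCare hydrogen peroxide cleaning system"; after Visit 4, "otherwise cleaning nightly with ClearCare". It does not say what the lenses are stored in on ordinary nights. The handling handout tells subjects to use Unique pH for both cleaning and storage. The Visit 2, 3 and 4 forms have an item for dispensing Unique pH, and no form has one for ClearCare.

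**The concern.** A placebo arm protects the conclusion only if the arms are compared. If the paired analysis in 10.2 is used as the test of Boost, the mean change in treated subjects is the Boost effect plus anything else that moves in the same direction after Visit 3. Placebo response is the obvious candidate, and it applies whichever lens care is used.

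A care-solution change is a second, conditional candidate. If 10.1 is followed, lenses may go from a ClearCare routine to a Unique pH overnight store just before Visit 4. That could affect Keratograph break-up and same-day comfort, by an unknown amount and in an unknown direction. If the handout is followed, nothing changes.

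Testing each arm separately and noting that only one is significant does not solve the problem, as the working shows. At stake is whether the study can support its own question, namely that Boost does something a sham soak does not.

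**Working it through.** **The plan's own figure.** There is no power calculation to reproduce. The only figure that can be checked is recruitment: 30 / (1 - 0.20) = 37.5, so 38, which lies inside the stated 35-40.

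**Inputs.** From 5.2: 30 completers analysed. Assumed, because the documents do not give them: 15 per arm, two-sided 5% level, normally distributed changes with SD 1, and a shift c equal in both arms. The values of c are illustrative.

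**Model.** Mean change in the Boost arm = b + c; in the placebo arm = c. A paired test in the Boost arm tests b + c = 0. A between-arm test tests (b + c) - c = b.

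**No Boost effect (b = 0)**, at least 40,000 simulated trials per row. Signed-rank: exact, n = 15, reject if the smaller rank sum is 25 or less. Rank-sum: 15 v 15, reject if U is 64 or less.

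| Shift c (SD) | Signed-rank significant, Boost arm | Boost arm improves, placebo arm not significant | Rank-sum between arms significant |
|---|---|---|---|
| 0 | 5% | 2% | 4-5% |
| 0.1 | 6% | 5% | 4-5% |
| 0.2 | 11% | 9% | 4-5% |
| 0.3 | 18% | 15% | 4-5% |
| 0.5 | 42% | 24% | 4-5% |

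Pooling both arms in one paired t-test (n = 30) is worse: 19%, 36% and 75% at c = 0.2, 0.3 and 0.5.

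**A true Boost effect (b = 0.8) with an adverse shift.** Signed-rank detection in the Boost arm falls from 80% at c = 0 to 42% at c = -0.3 and 18% at c = -0.5. Between-arm rank-sum power stays at 52-53%.

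**Difference detectable with 80% power** (noncentral t):
- Paired, n = 15: noncentrality d x √15; d = 0.78 SD.
- 15 v 15: noncentrality d x √(15 x 15 / 30) = d x √7.5; d = 1.06 SD.
- 20 v 10, if allocation were 2:1: d x √(200 / 30); d = 1.12 SD.
- 15 v 15, 5% split over two visits (0.025 each): 1.18 SD.
- 15 v 15, 5% split over four primary endpoints at two visits (0.05 / 8 = 0.00625 each): 1.40 SD.
- Rank-sum, 15 v 15, by simulation: 77% power at 1.06 SD; about 1.10 SD for 80%.

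**Are Visits 3 and 4 measured alike?** Acuity, Keratograph break-up, staining and the VAS for comfort at the time of asking are recorded the same way at both. The supplementary survey is not: insertion comfort and vision refer to an average day at Visit 3 but to that day at Visit 4, and end-of-day comfort and wearing hours are missing at Visit 4. CLDEQ-8 recalls the past week, so one day after treatment it mostly reflects the time before it. The Visit 3 and Visit 5 surveys do match.

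**The case against.** The strongest reply is that this is a pilot with an unfinished analysis section, not a plan to ignore the placebo arm. The analysis of variance and general linear models in 25.1 can carry an arm term, and 10.2 does at least describe results with and without Boost. That is fair as to intent. A reader might infer that the sponsor has decided against a between-arm test, and the documents do not say so. What stands is that the one specific inferential method is the paired one, and nothing directs the analyst to the randomized contrast.

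On lens care, the handout and the dispensing items point to Unique pH throughout, and the forms record the current cleaning solution at Visits 2 to 5. A reader might infer that the overnight solution does change before Visit 4. The texts conflict and do not settle this, so it is a secondary point. A between-arm test would cancel the change anyway if it is equal in both arms.

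Two limits also stand. Random day-to-day variation is not a bias: it is already in the paired test's standard error, and at zero shift the signed-rank test holds 5%. Nor does a between-arm test cure everything. The supplied text does not describe masking, and the surveys given to both arms refer to Boost treatment. If expectation differed by arm by 0.3 or 0.5 SD, the rank-sum test would reject 11% or 24% of the time with no Boost effect.

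**Conclusion.** The point holds. A randomized placebo arm exists, but the specified inference does not use it, and a within-person change from Visit 3 cannot attribute improvement to Boost. Under the assumptions above, a modest common shift of 0.2 to 0.5 SD raises the chance of a false Boost finding from 5% to between 11% and 42%; a between-arm test holds it at 4-5%. The direction of the argument does not depend on those assumptions, but the percentages do, since the documents give no SD, effect size or allocation ratio.

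Because 5.3 reserves the data for future power calculations, a reader might infer that the next trial will be undersized. For illustration only, sizing on 1.1 SD (0.8 Boost plus 0.3 shift) instead of 0.8 SD gives 13 per arm instead of 25. Section 5.3 does not say that a within-arm change would be used for this, so the figure shows what could happen, not what is planned.

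**What to change.** **Main change, in 10.2 and 25.1.** State that the Boost effect is tested by comparing change from Visit 3 to Visit 5, and from Visit 3 to Visit 4, between the randomized Boost and placebo arms, by a rank-sum test or by a general linear model with an arm term (a method 25.1 already lists). Report within-arm changes descriptively. At Visit 4 use only measures taken the same way at both visits: Keratograph break-up, acuity, staining and the VAS for comfort at the time of asking. Use CLDEQ-8 at Visit 5.

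**Minor change, in 10.1 and the handout.** State one regimen, naming the nightly cleaner and the overnight storage solution, so that the overnight solution is the same before Visits 3, 4 and 5 in both arms. Unique pH is the simplest choice because the handout and forms already use it; check it against the Boost kit instructions, which are not in the supplied text.

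**Cost.** About two sentences of analysis text and one line on care, with no new visit, product or measurement. The real price is the lower power shown in the working, and lower still if the 5% level is split over endpoints and visits. The paired test's advantage is genuine only if there is no common shift, which a study with a placebo arm should not assume.

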7.0 Multi-Site Research Communication – N/A

8.0 Study Timelines

8.1 Describe:

The total duration of the subjects' participation in the study will be approximately 5 months. It is anticipated that to enroll all study subjects it will take approximately 4-6 months. The estimated date for completion of this study is 11-12 months after the start of recruitment.

- Visit 1: The total time commitment required is approximately 100 minutes once informed consent has been commenced until the last test is completed.
- Visit 2: The total time commitment required is approximately 45 minutes until the last test is completed.
- Visit 3: The total time commitment required is approximately 85 minutes until the last test is completed.
- Visit 4: The total time commitment required is approximately 25 minutes until the last test is completed.
- Visit 5: The total time commitment required is approximately 25 minutes until the last test is completed.

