Questionnaires	Subjects will be asked to fill out the following questionnaires: • Contact Lens Dry Eye Questionnaire - 8 (CLDEQ - 8) • Visual analog scale (VAS) 0-100 • Secondary VAS scales at Visits 2-5 (unique to each visit) These questionnaires assess the level of eye and/or contact lens discomfort, and assess the subject perception of their habitual lenses and the coated lenses before and after Boost treatment.	No

Page 12 of 22 Revised: July 24, 2017

FULL PROTOCOL TITLE: An Evaluation of Tangible Boost Replenishing System on the Continued Efficacy of Tangible HydraPEG Rigid Gas Permeable Contact Lens Coating.

0.1.1/0.1	TT1 ' '11 ("1 1 1 1 1 1 1	NT
Scleral/Corneal lens fitting	The examiner will fit the subjects with scleral or corneal contact lenses using commercially available lens fitting sets (AVT scleral and corneal designs, AVT Technologies, CO). The lenses will be fit using the customary fitting procedure, where a diagnostic lens is applied to the eye, an over-refraction is performed, and then customized lenses are ordered with the over-refraction incorporated and any fitting parameters are altered based on the investigators' expertise. Once the lenses are dispensed, the subjects will be reminded of proper handling and cleaning techniques, and given a handout on lens care. In addition, at the 30-day visit subjects will be given instructions on the tangible boost kit or placebo that they are supplied.	No
Scleral/Corneal	The ordered rigid lenses will be applied to the eye of the	No
Lens Evaluation	subject by the investigator, after which the fit and vision will be evaluated. At this time, if the fit of the lens is adequate, the lenses will be dispensed. If there are additional parameter changes needed, they will be ordered at this time.	
Visual Acuity	The participant's vision in each eye will be measured with a high contrast visual acuity chart for the subjects' habitual lenses and the test lenses. The participant will be asked to cover one eye and read the chart, and this procedure will be repeated for the other eye.	No
Slit-lamp	The participant's front portion of each eye and contact	No
Examination	lenses will be examined with a lighted microscope. The participant will be asked to place his/her chin on the chinrest and place his/her forehead against the bar and look straight ahead. The instruments light will be shined onto the eye to visualize the ocular surface for approximately 2-3 minutes per eye.	

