*Note evalua 7.	: Habitual lens fit does not need to tion. Slit lamp exam (after lens remov OD	be re-evaluated at this (al) Lids and lashes Conjunctiva Sclera	visit. They ma	oy be removed without

[figure not shown]

Subject:	

Date: _____/_____

Evaluation of Tangible Boost Replenishing System

TOTAL Score: OD _____ OS ____

- 9. Fitting with Study Lenses:
 - a. Visual Acuity with Study Lenses (logMAR): Record # of letters seen

OD: _____ OS: OD: ____

b. Over refraction

OD _____

c. Slit Lamp Evaluation of Study Lenses
OD

Movement
Centration
Apical Clearance
Limbal Clearance
Scleral Landing Zone
Comments

10. Comments and suggested changes to lens parameters:

11. Need for New Lens order? \square_1 Yes \square_2 No \square_3 Maybe

Examiner Initials: _____

OS

TUC	\cap	AD C	SIIDEVOE	INSTITUTE
		AK	DUKLWCE	HINDHIULE

Subje	ect:		
Date:	/	/	

Base curv	e:	
Diameter	·	
Lens Pow	er:	
Limbal Pr	ofile:	
Landing Z	one Profile:	
13. Keratograph 14. Perform Kera	•	are dispensable)? \square_1 Yes \square_2 No
OD:	NIKavg-BUT "until blink" Level: NIKf-BUT "25 seconds" (first break up)s" (average break up)
OS:	NIKavg-BUT "until blink" Level: NIKf-BUT "25 seconds" (first break up)s" (average break up)
15. Contact lens	order form filled out? \Box_1	Yes \square_2 No \square_3 Not Applicable
16. Gift card give	n? \square_1 Yes	\square_2 No
17. Dispensed Le	nses? \square_1 Yes	\square_2 No

THE OCULAR SURFACE INSTITU	ΠH

Subject:		
Date:	_/	/

18. Dispensed Unique pH?	\square_1 Yes	\square_2 No			
19. Dispensed DMV?	\square_1 Yes	\square_2 No			
20. Dispensed PuriLens?	\square_1 Yes	\square_2 No			
21. Lens Dispense log filled out?	□ ₁ Yes	□ ₂ No			
22. Follow up appt made (30 days and +1 day)? \square_1 Yes \square_2 No					
23. Follow up appt dates: Appt 4 date:					
Appt!	5 date:				

Subject:		
Date:	_/	/

Evaluation of Tangible Boost Replenishing System

VISIT 3

ours of Rigid lens wear today:			
urrent Cleaning solution:			·
urrently wearing study lenses?	\square_1 Yes \square_2	No	
CLDEQ-8 a. CLDEQ-8 completed and verified	d: □₁ Yes	\square_2 No	CLDEQ-8 score:
'AS scale . VAS scale completed and verifie	ed: □₁ Yes	\square_2 No	VAS score:
o. Extended VAS scale completed:	\square_1 Yes \square_1 Yes \square_1 Yes \square_1 Yes	\square_2 No \square_2 No	removal: vision:
Medications a. Any changes in medications? b. If yes, please specify:	□ ₁		No
Visual Acuity with Study Lenses (lo	gMAR): Record # of	letters seen	
OD: OS:			

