Over refraction (spherical only) OD OS			
OD OS			os
OS Slit Lamp Evaluation of Study Lense	es Movemei Centratio Apical Cleara	on	os

Subject:		
ate:	/	
System		

	THE O	CULA	AR SURFACE INSTITUTE	Date://
	1	Eva	luation of Tangible Boost Replenishing	g System
			Scleral Landing Zone	
11.	Perforr	n Kera	atograph NIBUT	
		OD:	NIKf-BUT "until blink" (first break up) NIKavg-BUT "until blink" (average break up) Level:	
			NIKf-BUT "25 seconds" (first break up) NIKavg-BUT "25 seconds" (average break up) Level:	
		OS:	NIKf-BUT "until blink" (first break up) NIKavg-BUT "until blink" (average break up) Level:	
			NIKf-BUT "25 seconds" (first break up) NIKavg-BUT "25 seconds" (average break up) Level:	
12.	Are len	ises st	ill adequate to be worn? \square_1 Yes \square_2 No	
If no,	, please in	ndicat	ed parameter changes indicated below:	
13.			st Training and Video recording	
	а.	Video	o file name (camera)	
			o file name (go-pro)	
	c.	Video	is uploaded to share drive? \square_1 Yes \square_2 No	

UNIVERSITY of HOUSTON

THE OCULAR SURFACE INSTITUTE

[figure not shown]
Date:	/	/
		,

Evaluation of Tangible Boost Replenishing System

[figure not shown]
- d. Videos uploaded to Dropbox?
- \square_1 Yes □₂ No
- 14. **Tangible Boost or Placebo Kit Training**
 - a. Boost/Placebo dispensed? \square_1 Yes \square_2 No
 - b. Boost Log form filled out? \square_1 Yes \square_2 No
 - c. Boost Lot #:
- **15.** Removal of lenses and Slit lamp exam (after lens removal)

Corneal Fluorescein Staining (0-4 grading) 16.

TOTAL Score: OD _____ OS ____

- Dispensed Unique pH? \square_1 Yes \square_2 No **17.**
- 18. Dispensed DMV? \square_1 Yes \square_2 No
- **Dispensed PuriLens?** \square_1 Yes \square_2 No 19.

Sub	ject:		
Date: _	/	/	

20.	Gift card given?	□₁ Ye	S	□ ₂ No	1
21.	Follow up appt in 1 day	/?	□ ₁ Ye	!S	\square_2 No
22.	Follow up appt date:				

THE	OCIII	ΔR	SLIRFA	CF	INSTITU	ITE

Subject:		
Date:	_/_	/

VISIT 4

1.	Time of Day (military time) ::					
2.	Hours of lens wear today:					
3.	Current Cleaning solution:					
4.	Currently wearing study lenses? \Box_1 Yes	\square_2 No	0			
5.	CLDEQ-8a. CLDEQ-8 completed and verified:	□₁ Yes	□ ₂ No	CLDEQ-8 score:		
6.	VAS scale a. VAS scale completed and verified:	□ ₁ Yes	□ ₂ No	VAS score:		
	b. Extended VAS scale completed:	\square_1 Yes \square_1 Yes	\square_2 No \square_2 No \square_2 No \square_2 No \square_2 No	removal:vision:		
7.	Medications a. Any changes in medications? b. If yes, please specify:		es \square_2 No			

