Evaluation of Tangible Boost Replenishing System

	OD		OS
		_	e
		_ Comments	
erform Ker	atograph NIBUT		
OD:	NIKf-BUT "until k	olink" (first break up)	
	NIKavg-BUT "unt	til blink" (average break up)	
	Level:		
	NIKf-BUT "25 sec	conds" (first break up)	
	NIKavg-BUT "25	seconds" (average break up)	
	Level:		
OS:	NIKf-BUT "until k	olink" (first break up)	
	NIKavg-BUT "unt	til blink" (average break up)	
	Level:		
	NIKF-BLIT "25 see	conds" (first break up)	
	Level:		
			
ilit lamn eva	am (after lens remo	oval)	
iit iaiiip exe	OD	ovaij	OS
		Lids and lashes	
		Conjunctiva	
		Sclera	
		Cornea	
		Cornea 	
			

2

[figure not shown]

Subject: _____

[figure not shown]
Date: _____/_____

Evaluation of Tangible Boost Replenishing System

13. Corneal Fluorescein Staining (0-4 grading)

TOTAL Score: OD _____ OS ____

14. Gift card given? \square_1 Yes \square_2 No

Subject	•				
Dato:	1	1			

OPTIONAL VISIT FOR LENS RE-FITTING (TO BE USED IF THERE ARE FOLLOW-UP VISITS NEEDED FOR PROPER LENS FIT)

L .	Time of Day (military time) ::		
2.	Hours of Rigid lens wear today:		
3.	Current Cleaning solution:		
.	Currently wearing study lenses? \Box_1 Yes (if yes, evaluate lenses and \Box_2 No (if no, apply study lenses)	then remove and apply new ler	nses)
5.	Slit Lamp Evaluation of Study Lens test lenses if dispenses test lenses applied the habitual lenses	sed at last visit	ng evaluated)
	OD	Movement Centration Apical Clearance Limbal Clearance Scleral Landing Zone Comments	OS
.		of Study Lenses (only to be used test lenses applied today	d if test lenses for dispense were not
	OD	Movement Centration Apical Clearance Limbal Clearance Scleral Landing Zone Comments	OS
			Examiner Initials:

Page 1 of 6

Subject: _		
Date:	_/	/

DD:	OS:
Perform Ker	atograph NIBUT (to be performed only if lenses will be dispensed today)
OD:	NIKf-BUT "until blink" (first break up)
	NIKavg-BUT "until blink" (average break up) Level:
	NIKf-BUT "25 seconds" (first break up)
	NIKavg-BUT "25 seconds" (average break up) Level:
OS:	NIKf-BUT "until blink" (first break up) NIKavg-BUT "until blink" (average break up) Level:
	NIKf-BUT "25 seconds" (first break up) NIKavg-BUT "25 seconds" (average break up) Level:
Indicate CL (lesign parameter changes needed

CONTACT LENS QUESTIONNAIRE-8 (CLDEQ-8)

1. Questions about **EYE DISCOMFORT**:

- a. During a typical day in the past week, **how often** did your eyes feel discomfort while wearing your contact lenses?
 - 0 Never
 - 1 Rarely
 - 2 Sometimes

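### Break-up is read shortly after insertion at Visit 2 but after an unset number of hours worn at Visits 3 to 5, so the paired Visit 2-to-3 change could reflect wear that day rather than coating loss

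*Combined protocol and SAP*

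**What the plan says.** Section 9.1 lists the keratograph surface evaluation among four primary endpoints.

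**Visit 2.** The section 10.2 table describes the lens evaluation: "The ordered rigid lenses will be applied to the eye of the" subject by the investigator, who then checks fit and vision. On the Visit 2 worksheet the Keratograph items follow the study-lens fitting items and depend on whether the lenses "are dispensable". The optional refit worksheet has the same rule: break-up is "to be performed only if lenses will be dispensed today". Section 8.1 bounds the interval: "Visit 2: The total time commitment required is approximately 45 minutes until the last test is completed".

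**Visits 3 to 5.** The worksheets ask whether the study lenses are being worn and record time of day and hours of wear (Visit 4, item 2: "Hours of lens wear today"). Nothing sets a target wear time, a window or a clock time. For Visit 4, section 10.1 says only: "The subjects will report to the Ocular Surface Institute the next day for Visit 4".

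**Analysis.** Section 10.2 states: "Each individual will act as their own control to measure differences in pre and post contact lens measurements", using paired non-parametric statistics. For results with and without Boost it offers descriptive statistics. Section 25.1 compares baseline with test data and lists generic methods, including general linear models and regression. Neither section mentions hours worn or time of day. Boost or placebo is randomized at Visit 3 (section 10.1).

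**The concern.** The hypothesis in section 1.2 has two steps: the coating diminishes with wear over time, and Boost rebuilds it. Within a person, these correspond to the break-up change from Visit 2 to Visit 3 and from Visit 3 to Visit 4 or 5.

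For the first step the two readings are not taken under the same conditions. One lens has been on the eye for less than 45 minutes. The other may have been on for several hours. If break-up changes with hours worn in a day, that change is counted as 30-day coating loss.

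For the second step both readings have free wear time. A subject seen late in the day at Visit 3 and early the next day at Visit 4 could show an apparent gain on either solution. The comfort VAS that asks about the present moment is exposed in the same way.

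At stake is the reading of one primary endpoint and one comfort item in own-control comparisons, which are the only comparisons the plan describes.

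**Working it through.** **Step 1: Visit 2 wear time.** The section 10.1 table gives acuity 5, questionnaires 10, Keratograph 5, slit lamp 5, lens evaluation and dispense 20 minutes. 5 + 10 + 5 + 5 + 20 = 45 minutes, which reproduces section 8.1. Study-lens wear at the Visit 2 reading is therefore under 45 minutes; 0.5 h is used below.

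**Step 2: can recorded hours repair Visit 2 to 3?** Not well. On the Visit 2 worksheet the hours-of-wear item comes before the note on removing the habitual lenses, so it appears to describe those lenses. Study-lens wear at that reading is short for everyone, so wear time is almost inseparable from visit.

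**Step 3: illustrative size, Visit 2 to 3.** The documents give no slope, direction, SD or typical wear time. Assume no true loss, SD of the paired difference = 1, and break-up falling by b SD per hour worn. Then

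- false loss = b × (hours at Visit 3 − 0.5)
- noncentrality = false loss × √30, using the 30 analysed subjects of section 5.2, in a two-sided 5% paired t-test with 29 df.

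| b (SD/h) | Hours at Visit 3 | False loss (SD) | Rejection rate |
|---|---|---|---|
| 0.02 | 4 | 0.02 × 3.5 = 0.07 | 7% |
| 0.05 | 4 | 0.05 × 3.5 = 0.175 | 15% |
| 0.10 | 4 | 0.10 × 3.5 = 0.35 | 46% |

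Across 2 to 8 hours at Visit 3 the rate runs from 5% (b = 0.02, 2 h) to 98% (b = 0.10, 8 h). With equal wear time it is 5%.

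**Step 4: Visit 3 to 4.** Simulation of 20,000 trials with no treatment effect, assuming wear hours with SD 3 h at each visit and 15 v 15 subjects (the allocation ratio is not stated).

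| b (SD/h) | Visit 4 minus Visit 3, mean hours | Bias (SD) | Paired test, n = 30 | Boost v placebo |
|---|---|---|---|---|
| 0.02 | 0 | 0 | 5% | 5% |
| 0.02 | −4 | 0.02 × 4 = 0.08 | 7% | 5% |
| 0.05 | 0 | 0 | 5% | 5% |
| 0.05 | −4 | 0.05 × 4 = 0.20 | 18% | 5% |
| 0.10 | 0 | 0 | 5% | 5% |
| 0.10 | −4 | 0.10 × 4 = 0.40 | 49% | 5% |

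The added noise is √(1 + b² × (3² + 3²)). At b = 0.10 this is √1.18 = 1.086, so the SD of the change rises by about 9% at most.

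**Step 5: which comfort items are exposed.** At Visit 2 the CLDEQ-8 and VAS precede removal of the habitual lenses on the worksheet, and section 10.1 says the survey concerns current lenses. CLDEQ-8 recalls the past week. The Visit 3 and Visit 5 surveys ask about an average day, and the Visit 4 comfort item is tied to insertion. That leaves the momentary VAS, at Visits 3 to 5.

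**The case against.** The strongest reply is that Boost is judged against a concurrent randomized placebo. Any wear-time effect falls on both arms alike and cancels on average, and the Visit 2-to-3 interval lies wholly before randomization. This stands for a Boost v placebo contrast, where the check finds only modest noise. It does not protect the own-control comparisons in sections 10.2 and 25.1.

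A second reply is that no document says break-up worsens with same-day wear. That is correct. Direction and slope are assumptions, so the Visit 2-to-3 change could be confounded; it is not shown to be.

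A third is that hours worn are recorded, and section 25.1 lists models that could use them. Adjustment is possible for Visits 3 to 5, but it is not planned. At Visits 4 and 5 hours worn follow treatment and may respond to it, so adjustment could remove part of a real effect.

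Two stronger readings are tempting and not supported. A reader might infer that comfort, too, is scored minutes after insertion of the study lenses at Visit 2; the worksheet order and section 10.1 indicate that those scores describe the habitual lenses. A reader might also infer that the Visit 3-to-4 gain is biased by design. Both visits have free wear time, and nothing implies that Visit 4 is earlier in the day or in wear. The reverse order would push the change the other way.

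**Conclusion.** The point holds for break-up from Visit 2 to Visit 3. The difference in wear conditions is built into the schedule, so a paired change there cannot be attributed to coating loss alone. From Visit 3 to Visits 4 and 5, paired changes in break-up and in the momentary comfort VAS are exposed to bias if average hours differ, and to extra noise if they do not. A randomized Boost v placebo contrast is not biased. CLDEQ-8 and the average-day items are not affected.

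The size is unknown from the documents. Under the stated assumptions, false declaration of coating loss runs from 7% to 46% with Visit 3 at 4 hours, and from 5% to 98% over 2 to 8 hours. This is an inexpensive improvement to one primary endpoint in a 30-subject pilot. It does not undermine the randomized comparison.

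**What to change.** 1. Book Visits 3, 4 and 5 for each subject at the same clock time, within about 1 hour. Tell subjects to insert the lenses the same number of hours beforehand, within about 1 hour. Check this against the hours-of-wear item already on the worksheets.
2. Do not interpret the Visit 2-to-3 break-up change as coating loss unless Visit 3 break-up is also read at a wear time matching Visit 2. Record the interval from study-lens insertion to reading at both visits. A subject cannot arrive both hours into wear and newly inserted, so the matched reading needs reinsertion or insertion at the visit. Arriving in spectacles is feasible, because section 3.1 excludes people without a usable pair.
3. Use recorded hours worn only in a sensitivity analysis of break-up and the momentary VAS, because hours at Visits 4 and 5 follow treatment.

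The cost is less flexible appointments, plus a short extra wait at Visit 3 if the matched reading is added. Apart from that reading and its insertion time, no new data are needed.
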